5.3. Exclusion criteria

1. No written informed consent by parents and/or caregiver; no oral assent by participant.
2. Menarche, based on self-report
3. Presence of major systemic illnesses, e.g. diabetes, severe anemia (HB<8.0 g/l) as assessed by a medical doctor, upon initial clinical assessment.
4. History of acute or severe chronic disease.
5. Recent use of anthelmintic drug (within past 4 weeks).
6. Attending other clinical trials during the study.
7. Negative diagnostic result for hookworm eggs in the stool (< 100 EPG (total of the four slides) and/or only one Kato-Katz thick smear slide with more than one hookworm egg).

Participants who were diagnosed with a STH infection, but who were excluded from the study due to one or several of the above-mentioned exclusion criteria, including withdrawals, will be offered standard anthelmintic treatment (albendazole).

5.4. Criteria for discontinuation of trial

A subject can be discontinued from the study for the following reasons:

1. Withdraws from the study (this can happen anytime as participation is voluntary and there are no further obligations once a participant withdraws).
2. At the discretion of the Principal Investigator (PI) or co-PI, if the participant is not compliant to the requirements of the protocol.

Discontinued subjects will not be replaced. If, for any reason, a subject is discontinued from the study before the end of treatment evaluations, the safety procedures planned (adverse events monitoring) will be conducted.

Participants will stay all day at school for the morning and evening treatments. All drugs will be administered orally with a small amount of water in the presence of the investigator(s), and ingestion confirmed. This will be recorded with the time and date of dosing. On the first morning, depending on which treatment arm they were randomly allocated to, all participants will receive two tablets: one 100mg tablet (mebendazole or placebo) and one 500mg tablet (mebendazole or placebo). On the remaining five treatment points, also depending on which treatment arm they were allocated to, each participant will receive either one 100mg mebendazole tablet or one 100mg placebo tablet (Tables 2 and 3). Participants will be all day at school where the administration of mebendazole and capturing of AEs will take place. The morning dosing will occur when participants first arrive at school and the evening dosing will occur right before participants leave the school, approximately 10 hours later.

Table 3. Distribution of the administration of mebendazole and placebo in both groups.

	Day 1		Day 2		Day 3	
	Morning	Evening	Morning	Evening	Morning	Evening
Arm A	MEB 100 + plac 500	MEB 100	MEB 100	MEB 100	MEB 100	MEB 100

Arm B	MEB 500 + plac 100	plac 100	plac 100	plac 100	plac 100	plac 100
--------------	-----------------------	----------	----------	----------	----------	----------

Note: MEB 100, 100 mg of mebendazole; MEB 500, 500 mg of mebendazole; plac 100, placebo matching 100 mg mebendazole; plac 500, placebo matching 500 mg of mebendazole.

Subjects will be asked not to take any drugs other than those prescribed by the study medical team. After ingestion of the medication, which will be done at school, the subjects will be observed for 3 hours to ensure retention of the drug. Vomiting within 1-hour post-dosing will require re-dosing. The subjects will not be allowed more than one repeated dose. No re-administration will be needed for subjects vomiting after one hour. The site co-PI is responsible for drug accountability at the study site. Maintaining drug accountability includes careful and systematic study drug storage, handling, dispensing and documentation of administration. Any study product that is unused at the conclusion of the study will be destroyed.

5.6 Concomitant therapy

All medications taken one month before and during the study period until the last stool examination between day 14 and 21 (follow-up) must be recorded with indication, dose regimen, date and time of administration.

Medication(s)/treatment(s) permitted during the trial:

- Analgesics and antipyretics are allowed to be given to the subjects in case of fever, antiemetics to prevent nausea and vomiting and/or antibiotics to prevent or treat bacterial superinfection.

Medication(s)/treatment(s) NOT permitted during the trial:

- No other active drugs against helminths are permitted during the trial.

6. Safety assessments

Few adverse events have been reported following mebendazole administration. The most common reported adverse events are abdominal cramps, headache, diarrhoea, fever and fatigue [17, 23, 26]. The safety profile of mebendazole will be assessed through the recording, reporting and analysis of baseline medical conditions, adverse events and a physical examination. Participants will be encouraged to notify study staff of any adverse events that may occur outside of scheduled safety assessments. The medical doctor will be responsible for this part of the trial.

6.1. Adverse event definitions

The term “adverse event” could include any of the following events which develop or increase in severity during the course of the study, after administration of the study product:

- a) Any unfavourable and unintended signs, symptoms or disease temporally associated with the use of a medicinal product, whether or not considered related to the condition under study and the study product;
- b) Any abnormality detected during physical examination.

The medical conditions present at the initial trial visit that do not worsen in severity or frequency during the trial will not be defined as adverse events but as be considered baseline medical conditions. For the purpose of this trial, disease progression and relapse will be considered as treatment failure, not as an Adverse Event.

The observation time for adverse events starts when the treatment is initiated until day 5 (48 hours after last drug administration).

These data will be recorded on the appropriate CRF sections, regardless of whether they are thought to be associated with the study or the drug under investigation. Associated with the use of the drug means that there is a reasonable possibility that the event may have been caused by the drug (see also relatedness definitions below).

6.1.1. Severity grading

Adverse signs or symptoms will be graded by the Investigator as mild, moderate, severe or life threatening according to the following definitions:

Grade	Definition
1	Mild : the subject is aware of the event or symptom, but the event or symptom is easily tolerated.
2	Moderate : the subject experiences sufficient discomfort to interfere with or reduce his or her usual level of activity.
3	Severe : significant impairment of functioning: the subject is unable to carry out his or her usual activities.
4	Life threatening or disabling
5	Death related to adverse events

6.1.2. Relatedness

Relatedness will be assessed as defined below based on the temporal relationship between the adverse event and the treatment, known side effects of treatment, medical history, concomitant medication, course of the underlying disease and trial procedures.

Possibly related: an adverse event which can medically (pharmacologically/clinically) be attributed to the study treatment.

Unrelated: an adverse even which is not reasonably related to the study treatment. A reasonable alternative explanation must be available.

An adverse event that is determined to be related to the administration of a study product is referred to as an “adverse drug reaction.”

6.1.3. Expectedness

Expected adverse drug reaction: Any adverse event possibly related to the administration of mebendazole reported in the literature or on the drug package leaflet and listed in the consent form. These adverse events are detailed in the drug package leaflet (Appendix 3).

Unexpected adverse drug reaction: Any adverse event possibly related to the study product administration, the nature, frequency, specificity or severity of which is unanticipated and not consistent with the available risk information described for these drugs.

6.1.4. Serious adverse events

According to the ICH “Clinical Safety Data Management: Definitions and standards for expedited Reporting E2A” [54], a serious adverse event includes any event (experience) or reaction in any untoward medical occurrence that at any dose:

1. results in death;
2. is life threatening, meaning, the subject was, in the view of the Investigator, at immediate risk of death from the reaction as it occurred, *i.e.* it does not include a reaction that, had it occurred in a more serious form, might have caused death;
3. results in persistent or significant disability/incapacity, *i.e.* the event causes a substantial disruption of a person’s ability to conduct normal life functions;
4. requires in patient hospitalisation or prolongation of existing hospitalisation;
5. creates a congenital anomaly or birth defect (not relevant for this study);
6. is an important medical event, based upon appropriate medical judgment, that may jeopardize the patient or subject or may require medical or surgical intervention to prevent one of the other outcomes defining serious.

A “severe” adverse event does not necessarily meet the criteria for a “serious” adverse event. Serious adverse events are reported from consent to 48 hours post-treatment (Day 5).

Serious adverse events that are still ongoing at the end of the study period will be followed up to determine the final outcome.

The causality of any serious adverse event that occurs after the study period and its possible relatedness to the study treatment or study participation will also be assessed by investigators as described in section 6.1.2.

6.1.5. Suspected unexpected serious adverse reactions

A suspected unexpected serious adverse reaction (SUSAR) is an unexpected adverse drug reaction which also meets the definition of serious adverse events.

6.2. Methods of recording and assessing adverse events

Patients will be kept for observation for at least 3 hours following each morning treatment for any acute adverse events. During the reporting period, any unfavorable changes in the subject’s condition will be recorded as adverse events, whether reported by the subject or observed by the Investigator. In case of any abnormal finding, the local study physician will

perform a full clinical examination and findings will be recorded. An emergency kit will be available on site to treat any medical conditions that warrant urgent medical intervention.

In addition, patients will be also interviewed by a nurse and/or a physician about the occurrence of adverse events 24 hours after every morning treatment (before the next treatment) and 48 hours after the last treatment (day 5) (Table 2).

Information on all adverse events (onset, duration, intensity, seriousness and causality) will be immediately entered in the appropriate adverse event module of the case report form (CRF) which is considered as a source document. For all adverse events, sufficient information will be pursued and/or obtained so as to permit i) an adequate determination of the seriousness of the event (i.e. whether the event should be classified as a serious adverse event); ii) an assessment of the casual relationship between the adverse event and the study treatments (i.e. whether the event should be classified as an adverse drug reaction); and iii) an assessment of intensity of adverse events by the study physician.

All serious adverse events, unexpected adverse drug reactions, or SUSARs must be reported as described in Section 6.3.

6.3. Reporting of serious adverse events

Any study-related unanticipated problem posing risk of harm to subjects or others (including all unexpected adverse drug reactions), and any type of serious adverse event will be immediately (within a maximum of 24 hours after becoming aware of the event) notified to the study sponsor-investigator and co-PI:

[name]. [name] (Sponsor-investigator)

Swiss Tropical and Public Health Institute

[name]

[contact]

[contact]

E-mail: [contact]

[name] (Co-PI)

Public Health Laboratory Ivo de Carneri

[name]

[contact]

[contact]

[contact]
Email: [contact]

Within the following 48 hours, the local co-investigator must provide to study sponsor-investigator further information on the serious adverse event or the unanticipated problem in the form of a written narrative. This should include a copy of a completed SAE form, and any other diagnostic information that will assist the understanding of the event. In exceptional circumstances, a serious adverse event may be reported by telephone. In these cases, a written report must be sent immediately thereafter by fax or e-mail. Names, addresses and telephone for serious adverse event reporting will be included in the trial-specific SAE form. Relevant pages from the CRF may be provided in parallel (e.g., medical history, concomitant medications).

6.5. Safety reporting to Health Authorities and Ethics Committees

The sponsor-investigator will send appropriate safety notifications to Health Authorities in accordance with applicable laws and regulations. Additionally, this information will be provided to the 'Ethik Kommission Nordwest- und Zentralschweiz' (EKNZ, Switzerland) and 'Zanzibar Medical Research and Ethical Committee' (ZAMREC, Tanzania) according to national rules. Fatal or life-threatening serious adverse events or SUSARs will be reported within 24 hours followed by a complete report within 7 additional calendar days. Other serious adverse events and SUSARs that are not fatal or life-threatening will be filed as soon as possible but no later than 14 days after first knowledge by the sponsor.

7. Statistics

7.1. Definition of primary endpoint

Cure rate of mebendazole against hookworm is the primary endpoint in our study. Since this might be influenced by infection intensity, treatment groups will be equally balanced in terms of infection intensity by 2 levels of baseline infection intensity (light infections and moderate/heavy infections).

7.2. Justification of number of trial subjects

Sample size calculations for this study are based on the secondary objective comparing the efficacy of the two mebendazole regimens. Based on the published literature with special attention to studies conducted on Pemba Island, we assume that the cure rate of single dose mebendazole against hookworm infections is 20% compared to 40% in the triple treatment regimen [17, 33, 45, 46, 49]. To detect the difference with 80% power at a two-sided 5% significance level we require 79 participants per study arm. To account for potential loss to follow up (which was low in our previous studies in this setting) we aim to recruit in total 180 participants.

7.3. Description of statistical methods

The primary available case analysis will include all participants with primary end point data. In addition, an intention-to-treat analysis will be conducted considering all participants with missing endpoint data as treatment failure or all as treatment success to ensure that the results are not sensitive to potential loss to follow-up bias. CRs will be calculated as the percentage of egg-positive children at baseline who become egg-negative after treatment. EPG will be assessed by adding up the egg counts from the quadruplicate Kato-Katz thick smears and multiplying this number by a factor of six. The ERR will be calculated as:

$$ERR = 1 - \frac{\frac{1}{n} e^{\sum \log(EPG_{follow-up} + 1)} - 1}{\frac{1}{n} e^{\sum \log(EPG_{baseline} + 1)} - 1}$$

In the primary model we estimate the difference among CRs by using unadjusted logistic regressions. In a subsequent analysis an adjusted logistic regression (adjustment for age, sex, school, weight and strata) will be performed.

Geometric mean egg counts will be calculated for the different treatment arms before and after treatment to assess the corresponding ERRs. Bootstrap resampling method with 5,000 replicates will be used to calculate 95% confidence intervals (CIs) for ERRs and the difference between the ERRs.

Adverse events will be evaluated descriptively as the difference of proportion reporting adverse events before and after treatment.

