Measurements & procedures	
Two stool samples will be collected if possible on two consecutive days or otherwise within a maximum of 5 days apart. The medical history of the participating individuals will be assessed with a standardized questionnaire, in addition to a clinical examination carried out by the study physician on the treatment day.
 
Randomization of participants into the two treatment arms will be stratified according to intensity of infection. Participants will be interviewed before treatment for clinical symptoms and 3 hours after every morning treatment and 24 hours after every morning treatment about the occurrence of adverse events. The efficacy of the treatment will be determined 14-21 days post-treatment by collecting another two stool samples. All stool samples will be examined with duplicated Kato-Katz thick smears.

Statistical Analyses	
The primary analysis will include all participants with primary end point data (available case analysis). Supplementary, two sensitivity analyses will be conducted imputing all missing endpoint data as treatment failures or all as treatment success. CRs will be calculated as the percentage of egg-positive participants at baseline who become egg-negative after treatment. CRs will be compared by using unadjusted logistic regression. To assess model robustness with respect to covariates, adjusted logistic regressions (adjustment for age, sex, school, weight and strata) will be performed.
 
Geometric and arithmetic mean egg counts will be calculated for the different treatment arms before and after treatment to assess the corresponding ERRs. Bootstrap resampling method with 5,000 replicates will be used to calculate 95% confidence intervals (CIs) for ERRs and the difference of the ERRs.

GCP statement	This study will be conducted in compliance with the protocol, the current version of the Declaration of Helsinki, ICH-GCP E6 as well as all national legal and regulatory requirements.
Key explanation for the inclusion of	This study will be carried out in individuals aged 6-12 years old, since an infection with hookworm and other soil-transmitted

participants	helminths occurs most often in this age group.
Recruitment procedure	The study will be carried out in primary schools in Pemba Island, Tanzania.
Coverage of damages	Winterthur Police Nr. 4746321, National Insurance Cooperation of Tanzania LTD, GTA No: 00062.

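### The two planned missing-outcome analyses bound each regimen's cure rate but do not cover missing outcomes that differ by arm, so alone they cannot show that the regimen comparison is insensitive to loss

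*Combined protocol and SAP*

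**What the plan says.** Section 7.3 sets the main analysis population: "The primary available case analysis will include all participants with primary end point data". The comparison itself is a logistic model: "In the primary model we estimate the difference among CRs by using unadjusted logistic regressions".

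For missing outcomes, section 7.3 adds what it calls an intention-to-treat analysis, "considering all participants with missing endpoint data as treatment failure or all as treatment success to ensure that the results are not sensitive" to possible bias from loss to follow-up. The Synopsis (Statistical Analyses) describes the same plan: "two sensitivity analyses will be conducted imputing all missing endpoint data as treatment failures or all as treatment success". Both places have the same two scenarios, and each scenario applies one value to all missing children whatever their arm. The documents contain no arm-specific imputation, tipping-point analysis or multiple imputation.

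Section 7.2 bases the sample size on the comparison of the regimens, assuming that "the cure rate of single dose mebendazole against hookworm infections is 20% compared to 40% in the triple treatment regimen". On loss it says only: "potential loss to follow up (which was low in our previous studies in this setting) we aim to recruit in total 180 participants". Section 5.4 rules out replacing discontinued participants.

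**The concern.** An available-case comparison of two arms is biased when the missing children's outcomes depart from those observed in different ways in the two arms. A check on that bias has to let the missing outcomes differ by arm. Both planned scenarios hold them equal.

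The risk is a robustness statement that goes further than its test. A report could say that both sensitivity analyses agreed with the primary result and so loss to follow-up did not matter, although the scenario least favourable to that conclusion had not been examined. The comparison is formally a secondary objective, but it sets the sample size and is the subject of the primary model in section 7.3.

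**Working it through.** **Inputs.** Cure rates of 20% and 40%, 80% power, two-sided 5%, 79 per arm and 180 in total come from section 7.2. The figure of 90 per arm comes from the bag counts in section 5.5. The number lost is an assumption, because no rate is given, and it is varied below.

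**The plan's own figure.** Section 7.2 states: "To detect the difference with 80% power at a two-sided 5% significance level we require 79 participants per study arm". The unpooled normal approximation gives (1.960 + 0.842)² × (0.2×0.8 + 0.4×0.6) / 0.2² = 78.49, which rounds up to 79, so the figure is reproduced. The room for loss is 180 − 2×79 = 22 children, or 22/180 = 12.2%. This is inferred; the protocol does not state it as a loss rate.

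**Algebra.** Let n be the number randomised per arm, c_M and c_S the observed cures in the multi-dose and single-dose arms, and m_M and m_S the numbers missing. The risk differences (multi-dose minus single-dose) are:

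- all failure: (c_M − c_S)/n
- all success: (c_M + m_M − c_S − m_S)/n
- opposite, against multi-dose: (c_M − c_S − m_S)/n
- opposite, in favour of multi-dose: (c_M + m_M − c_S)/n

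If m_M = m_S, the two planned analyses give the same risk difference. In every case the lower bound lies m_S/n below the all-failure result and m_M/n below the all-success result. When both arms have losses, neither planned analysis reaches it.

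**Nine lost per arm.** Observed cures are 32/81 (multi-dose) and 16/81 (single-dose). Risk-difference intervals are Newcombe; odds ratios and p-values are Wald, as in unadjusted logistic regression.

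| Scenario | Multi-dose | Single-dose | Difference, points (95% CI) | OR | p |
|---|---|---|---|---|---|
| Available case | 32/81 | 16/81 | 19.8 | 2.65 | 0.007 |
| All failure (planned) | 32/90 | 16/90 | 17.8 (4.9 to 30.0) | 2.55 | 0.008 |
| All success (planned) | 41/90 | 25/90 | 17.8 (3.7 to 30.9) | 2.18 | 0.014 |
| Opposite, against multi-dose | 32/90 | 25/90 | 7.8 (−5.8 to 20.9) | 1.43 | 0.26 |
| Opposite, for multi-dose | 41/90 | 16/90 | 27.8 (14.3 to 39.9) | 3.87 | 0.0001 |

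**Varying equal loss**, with observed rates kept close to 40% and 20%:

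| Lost per arm | All failure p | All success p | Opposite, against multi-dose |
|---|---|---|---|
| 4 | 0.006 | 0.008 | 34/90 vs 21/90, p=0.037 |
| 5 | 0.006 | 0.008 | 34/90 vs 22/90, p=0.055 |
| 9 | 0.008 | 0.014 | 32/90 vs 25/90, p=0.26 |
| 11 | 0.008 | 0.015 | 32/90 vs 27/90, p=0.43 |

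Eleven per arm is the full allowance (90 − 79). For every equal loss from 1 to 14 per arm, both planned analyses stay significant (p ≤ 0.024). The opposite imputation loses significance from 5 per arm (5/90 = 5.6%).

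**Unequal loss.**

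- 4 lost on multi-dose and 18 on single-dose: available case 34/86 vs 14/72, p=0.007; all success 38/90 vs 32/90, OR 1.32, p=0.36. Here the planned pair does signal a problem.
- 16 lost on multi-dose and 6 on single-dose: all failure 30/90 vs 17/90, p=0.029; all success 46/90 vs 23/90, p=0.0005; opposite imputation 30/90 vs 23/90, OR 1.46, p=0.25. Here it does not.

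**The case against.** The strongest defence starts from the primary objective, which is each regimen's own cure rate. For that, all failure and all success are exact lower and upper bounds on the observed proportion: with 9 lost per arm, 16/90 to 25/90 for single dose and 32/90 to 41/90 for multi-dose. The stated purpose speaks of loss-to-follow-up bias without mentioning differential loss. If arm-level rates are reported under both scenarios, a reader can form the opposite contrasts by subtraction. All of this stands. However, the plan makes its claim for the results in general, the comparison is among them, and nothing commits the report to the cross contrasts.

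The second defence is that arm-dependent loss is unlikely. The trial is double-blind with matching placebo, both arms have the same six observed dosing times, and there is a single follow-up window at 14-21 days. The protocol describes earlier loss in this setting as low. The worst case at 9 per arm needs every lost single-dose child to be cured and every lost multi-dose child not to be. This also stands and reduces the practical weight. It makes bias less likely, but it does not test for it.

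A reader might infer three stronger things that the documents do not support:

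- *That the planned pair can never reveal an effect of differential loss.* It can when the number lost differs by arm, as the 4 and 18 example shows.
- *That the imputation bounds cross zero.* At 9 lost per arm they are 7.8 and 27.8 points, both positive. Only the confidence interval around the lower one includes zero.
- *That the planned analyses show no movement at all.* That is true only of the risk difference under equal loss, where the two agree with each other but still sit below the available-case value. On the planned logistic scale the odds ratio goes from 2.65 to 2.55 and 2.18.

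**Conclusion.** The point holds for the regimen comparison. The two planned analyses do not let missing outcomes differ by arm, so agreement between them cannot by itself support the statement that the comparison is insensitive to loss. For each arm's own cure rate the pair is adequate.

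The size depends on a loss that the protocol does not quantify. At the planning rates and 90 per arm, four or fewer lost per arm would leave even the opposite imputation significant, and the added analysis would then support the robustness claim. From five per arm, less than half of the inferred 12.2% allowance, the planned pair reports robustness while the opposite imputation does not. These thresholds assume equal loss and observed rates near 40% and 20%; other observed rates would move them. The primary estimate, the sample size and the conduct of the trial are unaffected.

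**What to change.** Keep both planned analyses and describe them as bounds on each arm's cure rate. In section 7.3 and the Synopsis, add:

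1. two opposite-direction imputations for the comparison: missing as success in the single-dose arm and failure in the multi-dose arm, and the reverse;
2. a tipping-point table over the number of missing children assumed cured in each arm, showing the estimated difference and whether the conclusion changes;
3. a sentence saying that the robustness statement for the regimen comparison rests on items 1 and 2.

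The table is small: with 9 lost per arm it has 10 × 10 = 100 cells. The cost is a few lines of text and code, with no new data. The downside is that the opposite imputations are wide and implausible as descriptions of what happened, especially in a blinded trial that expects little loss. They should be presented as outer bounds, with the tipping-point table beside them so that readers can judge how extreme the missing outcomes would have to be.

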4.3. Measure to minimize bias

Study participants eligible for treatment will be randomly assigned to one of the two treatment arms using a computer-generated stratified block randomization code. The random allocation sequence with varying random blocks of four or eight and stratified by 2 levels of baseline infection intensity (light: 1-1999 EPG, and moderate plus heavy: ≥ 2000 EPG hookworm infections) will be provided by a statistician. Both treatment arms will have an equal number of participants with light infection intensity, although the number of light versus moderate/heavy infections are not expected to be equal in each arm, depending on the distribution of infection intensity in the recruited cohort. The codes will be held in a locked cabinet at the Swiss Tropical and Public Health Institute. A copy of this code will be kept in a sealed envelope by one of the co-investigators (will only be unblinded in case there is a serious adverse event, determined by the principal investigator upon consultation with the co-investigators). The blinding will be maintained throughout the trial until data entry and processing are complete and the data have been verified. Following release of the final data, the randomization codes will be released.

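### The primary cure-rate model leaves out the stratum used in randomisation, at a small power cost if infection intensity predicts cure, and it gives an odds ratio where section 7.3 promises a difference

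*Combined protocol and SAP*

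**What the plan says.** Section 4.3 describes a computer-generated sequence, blocked and "stratified by 2 levels of baseline infection intensity", with a cut at 2000 EPG. Section 7.1 gives the reason: "Since this might be influenced by infection intensity, treatment groups will be equally balanced in terms of infection intensity".

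For the analysis, section 7.3 states "In the primary model we estimate the difference among CRs by using unadjusted logistic regressions". The synopsis (Statistical Analyses) is consistent with this: "CRs will be compared by using unadjusted logistic regression".

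The stratum is not absent from the plan. Section 7.3 continues: "In a subsequent analysis an adjusted logistic regression (adjustment for age, sex, school, weight and strata) will be performed". The synopsis makes clear that this model is a robustness check.

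The sample size in section 7.2 is set on the cure-rate scale: "we assume that the cure rate of single dose mebendazole against hookworm infections is 20% compared to 40% in the triple treatment regimen", with 80% power at a two-sided 5% level, giving 79 per arm and a recruitment target of 180. Section 7.2 calls the between-arm comparison a secondary objective, although it drives the sample size and section 7.3 calls its model the primary one.

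**The concern.** Two things do not fit together.

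**Design and analysis.** Stratified blocks remove most of the chance imbalance in intensity between the arms. The true sampling variance of the arm contrast then reflects only the variation within strata. An unadjusted model still counts the variation between strata as noise. If the stratum predicts cure, the standard error is too large, the test runs below its nominal level and some power is given away.

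**Effect measure.** A logistic model with arm as its only term estimates a log odds ratio. Section 7.3 says it estimates a difference in cure rates. Nothing in the plan says how that difference and its confidence interval are to be obtained, and nothing names the odds ratio as the reported measure. For the egg reduction rates, a secondary endpoint, the same section does specify a bootstrap interval for the difference.

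At stake are a modest amount of precision and a clear statement of what the main between-arm result will be.

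**Working it through.** **1. The plan's own figure.** Inputs from section 7.2: 20% and 40%, 80% power, two-sided 5%.

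- Difference scale, unpooled variance: (1.960 + 0.842)² × (0.2×0.8 + 0.4×0.6) / 0.2² = 78.5, rounded up to 79. This reproduces the stated number.
- Log odds ratio scale (Wald): (1.960 + 0.842)² × (1/0.16 + 1/0.24) / (ln 2.667)² = 85.0.

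The trial was therefore sized as an unadjusted comparison of two proportions on the difference scale.

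**2. The two effect scales.** The odds ratio is (0.4/0.6)/(0.2/0.8) = 2.67. Suppose 18/90 and 36/90 children are cured.

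- Odds ratio: the standard error of its log is √(1/36 + 1/54 + 1/18 + 1/72) = 0.340, so 2.67 (95% CI 1.37 to 5.19).
- Difference: the standard error is √(0.24/90 + 0.16/90) = 0.0667, so 20 points (95% CI 6.9 to 33.1).

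**3. Why the size of the loss depends on the stratum effect.** The documents give neither the share of children in each stratum nor the effect of stratum on cure, so both are assumed. Take a 50/50 split.

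- Stratum odds ratio 8: cure is 34.0% (light) and 6.0% (heavier) on the single dose, and 62.7% and 17.3% on the three-day regimen. The between-stratum variance is 0.14² + 0.227² = 0.071, out of 0.16 + 0.24 = 0.40, or 18%. The unadjusted standard error is about 1/√0.82 = 1.10 times what it should be.
- Stratum odds ratio 2: cure is 25.4% and 14.6%, against 48.2% and 31.8%. The between-stratum variance is 0.054² + 0.082² = 0.0096, or 2.4% of 0.40. The inflation of the standard error is about 1%.

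**4. Simulation at 90 per arm.** 40,000 trials per scenario, exact 1:1 balance within strata, Wald tests. Power is at 20% against 40% overall; size is at a common cure rate of 30%. Each cell shows unadjusted / stratum-adjusted, in %.

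| Light share | Stratum OR | Power | Two-sided size |
|---|---|---|---|
| 50% | 1 | 83.6 / 84.1 | 4.60 / 4.83 |
| 50% | 2 | 83.9 / 84.9 | 4.56 / 5.04 |
| 50% | 4 | 85.0 / 87.4 | 3.80 / 5.09 |
| 50% | 8 | 85.7 / 90.1 | 2.84 / 4.92 |
| 70% | 1 | 83.3 / 83.7 | 4.75 / 4.93 |
| 70% | 2 | 84.1 / 85.0 | 4.60 / 4.99 |
| 70% | 4 | 84.6 / 86.5 | 4.18 / 5.15 |
| 70% | 8 | 84.9 / 87.7 | 3.51 / 4.85 |
| 90% | 1 | 83.4 / 83.9 | 4.59 / 4.81 |
| 90% | 2 | 83.5 / 84.0 | 4.81 / 5.05 |
| 90% | 4 | 84.0 / 84.8 | 4.38 / 4.79 |
| 90% | 8 | 84.2 / 85.3 | 4.28 / 4.72 |

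The gap of 0.4 to 0.5 points at odds ratio 1 is not a stratum effect. An unadjusted likelihood-ratio test closes it (84.2, 83.9 and 84.0%), so it comes from the Wald test itself.

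**5. Simulation at 170 evaluable children** (20% or 40% in the heavier stratum; 170 is an assumption, since the plan states no loss rate).

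- No stratum effect: power 82.0% unadjusted, 82.1% adjusted; size 4.7% for both.
- Stratum odds ratio 2: adjustment gains 0.4 to 0.7 points.
- Stratum odds ratio 4: gains 1 to 2 points.
- Stratum odds ratio 8: gains 1.4 to 3.5 points; unadjusted size about 3.5 to 4.1%.

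**6. At exactly 79 evaluable per arm.** Unadjusted power is 78.6 to 81.0%, and adjusted power 78.8 to 86.0%. The lowest unadjusted value occurs with no stratum effect, so the omitted stratum does not cause it. The largest gain is 5 points (81.0 to 86.0%), at a 50/50 split and odds ratio 8.

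**7. Comparability of the planned models.** In these scenarios the median stratum-adjusted odds ratio is 2.7 to 3.3, against 2.67 marginally. Odds ratios are non-collapsible, so the primary and robustness models do not estimate the same quantity even when both are correct.

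**The case against.** The strongest defence is that little is lost and much is already covered.

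- **The stratum effect is only a possibility.** Section 7.1 says cure might depend on intensity and gives no size. This stands: conservatism and power loss are conditional, and with no stratum effect they vanish.
- **A model with the stratum is prespecified.** This also stands, and it would be wrong to infer that no planned analysis uses the stratum. But that model is labelled a robustness check and adds four further covariates. No planned model has arm and stratum alone, and because of non-collapsibility a shift in its odds ratio cannot simply be read as a lack of robustness.
- **The difference is recoverable.** With arm as the only term, the fitted probabilities equal the observed cure rates, which section 7.3 says will be calculated. So a reader should not conclude that the plan cannot deliver a difference. What is missing is a stated effect measure and a method for its interval.
- **The comparison is a secondary objective.** True by label, but the sample size rests on it and section 7.3 calls its model primary.
- **Part of the conservatism belongs to the Wald test.** Correct: size is about 4.6 to 4.8% with no stratum effect at all.

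**Conclusion.** The point holds as a modest efficiency and clarity issue. The primary model omits the factor on which randomisation was stratified, and it is said to estimate a quantity that its coefficient does not give.

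The cost of the omission depends on assumptions the documents do not settle: the split between strata, and the strength of the association between intensity and cure. Over the range examined, power given up runs from nil to a few points, and reaches 4 to 5 points only with a 50/50 split and a stratum odds ratio of 8.

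Two stronger readings should be resisted. A reader might infer that ignoring stratification inflates the false-positive rate; any departure from 5% is downwards. A reader might also infer that the trial is underpowered as a result. The 79 per arm was itself computed without adjustment, and unadjusted power is above 80% at 170 evaluable children and at least 83% at 180. The loss is relative to a better test, not to the plan.

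The mismatch of effect scale needs no assumption about the stratum. It follows from the wording of section 7.3 and the reproduction of 79 per arm.

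**What to change.** In section 7.3 and the synopsis:

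- Make the primary between-arm model a logistic regression on arm plus the two-level randomisation stratum.
- From that model, report the standardised (marginal) cure-rate difference with a 95% CI, and name the interval method. A Mantel-Haenszel stratified risk difference would serve equally well.
- Report the odds ratio beside it, labelled as conditional on stratum.
- Keep the unadjusted model and the already planned model with all five covariates as sensitivity analyses. Compare the three on the difference scale so that non-collapsibility does not obscure the comparison.

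The cost is a few lines of text and one model term, using a variable that randomisation already requires. No new data and no change in sample size are needed. The one small drawback is that the conditional odds ratio will differ from the unadjusted one; leading with the marginal difference resolves that. The change should be made before the randomisation codes are released, so that model and scale are not chosen after seeing results.
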